Anal cancer (AC) is a rare malignancy, with approximately 200 new cases diagnosed annually in Denmark¹. This cancer predominantly affects women and is strongly associated with human papillomavirus (HPV) infection. The standard treatment for localized anal cancer (AC) is chemoradiotherapy (CRT). In Denmark, the standard approach involves delivering a total radiation dose of 54-60 Gy to the primary tumor and pathological lymph nodes, administered in fractions of 1.8-2 Gy per session. Elective lymph node regions are typically treated with a lower dose of 45-50 Gy². This regimen has proven highly effective, achieving excellent rates of disease control and survival^{3,4}. However, the long-term adverse effects of CRT remain a critical concern, one of them being gynecological and sexual health. These domains are often underreported and insufficiently addressed in routine clinical practice⁵.

Radiotherapy for AC frequently affects adjacent organs at risk (OAR), including the female genital tract. This exposure can result in complications such as vaginal stenosis, dyspareunia, and broader sexual dysfunction⁶. The reported prevalence of these complications varies widely across studies. For example, some investigations report sexual dysfunction in up to 85% of female survivors (Yerramilli et al., 2019)⁷, while others, such as De Francesco et al. (2016)⁸, note that only 2 out of 21 women identified an impact on sexual relationships.

The wide variation in prevalence rates may be attributed to methodological heterogeneity in measuring vaginal symptoms. Many studies rely on differing assessment tools, complicating efforts to synthesize findings. Furthermore, research often focuses on sexually active individuals, potentially underestimating symptom prevalence among sexually inactive patients and leaving a significant proportion of affected women unrepresented. Additionally, physician-reported outcomes are seldom based on physical examinations, further undermining the reliability and comprehensiveness of available data. This lack of standardized assessment methods highlights a critical knowledge gap and adds to the variability in reported outcomes.

Another significant challenge is the poorly understood relationship between radiation dose and vaginal toxicity after AC treatment, which complicates the establishment of clinically relevant dose constraints for sexual OARs. While some studies have explored dose-response relationships, findings remain inconsistent. For instance, Arzola et al. (2023)⁹ suggested that keeping the dose to 50% of the anterior vaginal wall <48 Gy could reduce the risks of impaired sexual function. Similarly, Son et al. (2015)¹⁰ proposed that mean vaginal doses below 43 Gy were associated with a reduced risk of severe vaginal stenosis. Conversely, other studies, including Joseph et al. (2016)¹¹, have failed to demonstrate significant correlations between vaginal dose metrics and sexual dysfunction outcomes measured through standardized instruments like the EORTC-CR29.

These discrepancies underscore the urgent need for further research into the mechanisms and clinical predictors of gynecological morbidity and sexual health following CRT. Exploring dose constraints could pave the way for enhanced survivorship care in women treated for anal cancer.

Secondary preventive strategies

Despite well-documented risks, the implementation of secondary preventive strategies for mitigating long-term complications still needs to be revised. Evidence supports that vaginal dilator use and sexual counseling can reduce the risk and severity of late effects following radiation therapy¹²⁻¹⁵. Currently, all Danish cancer treatment centers routinely provide vaginal dilators to female patients after the end of radiation therapy with basic information on their use. The general recommendation

is to initiate dilator use approximately six to eight weeks post-radiation treatment, with a suggested frequency of three times per week.

In Denmark, patients can be referred to specialized sexual health nurses for counseling on sexual dysfunction after treatment for anal cancer. Additionally, all centers have access to late-effects clinics for further support. However, systematic documentation regarding the type and extent of counseling provided is lacking, as is a comprehensive insight into patients' satisfaction with these services. Greater patient involvement in refining guidance and care strategies is crucial to meeting unmet needs and enhancing survivors' quality of life.

Purpose

The primary objective of this study is to examine the prevalence and severity of vaginal morbidity in women following treatment for localized anal cancer and to identify predictive factors, including the potential dose-response relationship between radiation exposure and morbidity. Furthermore, the study seeks to investigate possible correlations between vaginal morbidity and patient-reported sexual dysfunction.

The secondary objective is to investigate patterns of care related to managing gynecological toxicity and sexual dysfunction, including the use of dilators and hormone therapy. The study also evaluates patient satisfaction with the guidance provided to identify areas for improvement, aiming to support the development of standardized, high-quality practices that ensure consistent and patient-centered care across Denmark's three anal cancer treatment centers.

Study design

This is a national multicenter, cross-sectional study that collects quantitative and qualitative data from gynecological examinations, questionnaires, and semi-structured interviews.

Study population

Inclusion criteria:

- Female patients aged 18 or older.
- Diagnosed with AC and treated with CRT with curative intent.
- 6–36 months post-CRT.
- Willing and able to provide informed consent.

Exclusion criteria:

- History of pelvic radiotherapy for conditions other than the current diagnosis.
- Treatment with electron beam radiotherapy.
- Non-Danish speaking

Inclusion procedures

Participants will be identified during follow-up consultations (6-36 months) at Aarhus University Hospital, Vejle Hospital, and Herlev and Gentofte Hospital. When a potential participant is identified, the treating physician responsible for the consultation will provide both oral and written information about the study. Participants will be informed that they have the right to have a companion or support person present during the initial oral information consultation. To ensure sufficient time for consideration, participants will be offered an inclusion consultation at least 24 hours after the initial

consultation. During this consultation, further questions can be addressed, and participants are welcome to bring a companion or relative.

Written informed consent will be obtained at this inclusion consultation before study participation. Patients will be assured of confidentiality. Patients will be informed that their participation is entirely voluntary and that they can withdraw their consent at any time without affecting their future care.

If they consent, the gynecological examination will either be performed shortly after consent or scheduled for their next follow-up visit, depending on patient preference and clinical feasibility.

Endpoints

Primary endpoint:

- Prevalence of vaginal stenosis grade 2 or higher.

Secondary endpoints:

- Gynecological findings: vaginal elasticity, adhesions, telangiectasias, ulceration, and bleeding.
- Radiation Dose to sexual organs at risk
- Patient-reported outcomes on sexual health issues
- Pattern of care; dilator use, lubrication, hormone treatment(local/systemic), received specialized sexual counseling.
- Patient satisfaction with the existing sexual rehabilitation program

Data collection

1. Sociodemographic data

Sociodemographic data will be collected via a case report form (CRF) during the consultation where the gynecological examination is performed. This data includes age, smoking status, menopausal status, relationship status, WHO performance status, and comorbidities. (first part of Appendix 1)

2. Clinical data

Clinical data will be extracted from medical records. They will encompass details of the anal cancer diagnosis, including tumor location (with specific information on vaginal invasion if present), tumor volume and length, histological type, and TNM classification. Information about the treatments received will be detailed, including radiation dose and fractionation schedule, as well as chemotherapy regimens. Additionally, data on any salvage surgery or recurrence will be collected, along with details of any subsequent treatments provided for the recurrence. Access to these records will be granted to the principal investigator and relevant regulatory authorities for research purposes, including monitoring, quality control, and compliance with required oversight.

3. Gynecological examinations:

Comprehensive vaginal morbidity will be assessed using an electronic case report form, as detailed in Appendix 1. The morbidity assessment form is based on vaginal morbidity documentation following radiotherapy for cervical cancer, as described by Kirchheiner (2012)¹⁶. This methodology has also been employed in Suval (2023)¹⁷.

To ensure uniform grading of vaginal morbidity across the study sites, a dedicated seminar will be held before the initiation of patient inclusion. This seminar will involve all relevant physicians responsible for assessments at the three participating centers to align understanding and grading practices, minimize inter-observer variability, and ensure consistency in evaluations throughout the study.

4. Patient-reported outcome measures:

Electronic surveys will be sent following the control visit where the gynecological examination is performed. A reminder email will be sent after one week if a response is missing. If the patient cannot access the survey electronically, it will be handed in on paper form during the consultation and entered electronically afterward.

The survey will include validated questionnaires: the European Organization for the Research and Treatment of Cancer Quality of Life Core Questionnaire (EORTC QLQ-C30) with the Anal Cancer Module (EORTC-QLQ-ANL27), EORTC Sexual Health Questionnaire (EORTC-QLQ-SH22), and Female Sexual Function Index (FSFI). See Appendix 2 for details on these questionnaires.

In addition to the questionnaires mentioned, there will be questions regarding patterns of care, see Appendix 3

5. Radiation Dose parameter:

The principal investigator will retrospectively delineate the vagina on therapy scans from the included participants in accordance with applicable delineation guidelines. Based on this, a retrospective analysis of dose-volume histograms will be performed to identify correlations between vaginal morbidity and radiation exposure.

6. Interviews:

Semi-structured interviews with early participants will be conducted over the telephone using the interview guide provided in Appendix 4. The interviews will be conducted with notes taken on themes and quotes during the sessions for further analysis.

Data management

All data will be entered into a secure electronic database (REDCap) hosted at Aarhus University Hospital. Compliance with GDPR and Danish data protection regulations will be ensured.

Sample size and statistical analysis plan

Sample size

Annually, approximately 120 women in Denmark undergo treatment for anal cancer, with roughly stage distributions of 25% (Stage I), 52% (Stage II), 17% (Stage III), and 6% (Stage IV)¹⁸. Using survival data from the RTOG 98-11 trial¹⁹, we calculated 1-, 2-, and 3-year survival rates assuming a linear decline from 100% survival at treatment initiation to the reported 5-year survival rates of 82% for Stage I, 74% for Stage II, 57% for Stage III, and 42% for Stage IV. From these calculations, women treated three years ago contributed approximately 99 women alive, those treated two years ago contributed 106, and those treated one year ago contributed 113, yielding a total of 318 women who have received treatment for anal cancer within a period of three years are alive and eligible for follow-up. Given the sensitive nature of topics such as gynecological toxicity and sexual dysfunction,

we conservatively estimate a participation rate of 30%. This results in an expected inclusion of 80 participants.

This sample size of approximately 80 participants will allow us to achieve 80% statistical power to detect a correlation between radiation dose and vaginal stenosis, with a significance level of 0.05 and an assumed moderate correlation coefficient of $r=0.3$. This power calculation ensures that the study is adequately designed to investigate the potential dose-response relationship.

For the semi-structured interview sub-study, 20 participants are initially included to explore patient satisfaction with the sexual rehabilitation program. Thematic analysis will guide data collection and analysis, following an iterative approach to identify saturation. Saturation is defined as the point where no new themes, patterns, or insights emerge, ensuring data utility is maximized.

If thematic saturation is not reached after the initial sample, additional participants will be included in batches of 5 participants. This approach ensures robust, comprehensive findings aligned with the research objectives while maintaining methodological rigor.²⁰

Statistical analysis plan

Vaginal stenosis grade 2 or above, will be calculated as the proportion of participants meeting the criteria out of the total number of participants. A 90% confidence interval (CI) will be used to indicate the uncertainty surrounding the prevalence estimate.

Physician-reported vaginal outcomes: Variables such as adhesions, elasticity, telangiectasias, ulcerations, and bleeding will be summarized using descriptive statistics

Patient-reported outcomes (PROs): Data from the Female Sexual Function Index (FSFI), EORTC-QLQ-SH22 and EORTC-QLQ-C30 with the ANL24 supplement will be analyzed. Scores will be calculated according to the respective guidelines, transforming raw data into standardized scores. Comparisons across groups (e.g., stenosis vs. no stenosis) will be made using appropriate tests such as t-tests or Mann-Whitney U tests.

Dose-response relationship: This will be explored using logistic regression, assessing the relationship between radiation dose and vaginal stenosis grade 2 or above. A dose-response curve will also be generated using spline regression to visualize potential non-linear relationships.

Patient care satisfaction: Data from semi-structured interviews will be analyzed using thematic analysis to identify key themes and patterns related to patient satisfaction with guidance and counseling on gynecological and sexual issues post-treatment. Notes will be coded in an exploratory manner, allowing themes to emerge from the data and ensuring a comprehensive understanding of patient experiences and perspectives.

All analyses will be conducted using a predefined statistical significance level of 0.05. Results will be reported with appropriate measures of uncertainty, such as confidence intervals. Quantitative data analyses will be performed using StataSE18 software, and qualitative data will be analyzed using NVivo14 software.

Study schedule (tentative)

Protocol approved: Awaiting

Inclusion start: 01.05.2025

Inclusion end: 01.05.2026 2026

End of data collection: June 2026

Data analysis and interpretation: Fall 2026

Plans for dissemination and reporting

The findings of this study will be disseminated to ensure academic and public access to the results. Planned activities include publishing study results in peer-reviewed scientific journals and presentations at national and international conferences focusing on oncology, radiation therapy, and survivorship care. All results, whether positive, negative, or inconclusive, will be published to contribute to the broader evidence base.

Efforts will also be made to communicate the key findings in layperson-friendly formats, such as patient-oriented brochures or updates to clinical practice guidance, to benefit survivors and healthcare professionals involved in anal cancer care.

The principal investigator ([name]) will be first author on the papers. All investigators will be invited for a co-authorship according to the Vancouver regulations

Ethical issues, safety aspects, and complications

The study will adhere to ethical standards and obtain approval from relevant medical ethics committees. All participants will provide written and oral informed consent before inclusion in the study. No serious complications are expected from the gynecological examination. In the short term, some individuals may experience temporary discomfort during the procedure. Additionally, discussing intimate topics may be emotionally distressing for some participants. While no long-term risks are known, unforeseen burdens related to participation cannot be entirely ruled out. If you experience discomfort, you have the right to withdraw from the study at any time or choose not to answer specific questions. Emphasis will be placed on minimizing discomfort and safeguarding participant confidentiality. The anticipated benefits of the research include improved treatment outcomes and enhanced quality of life for future patients.

Funding and Financial Disclosure

The study is investigator-initiated, with the investigator independently designing and conducting the research.

Participants in this study are covered by the Danish Act on Complaints and Compensation within the Healthcare System, and any complaints can be submitted to the Danish Agency for Patient Complaints in accordance with applicable regulations.

A grant from the Independent Research Fund Denmark (DKK 2.112.424) covers expenses related to the project-specific investigations. The grant funds are administered by Aarhus University. None of the researchers involved have financial interests in the project or affiliations with the funding provider. No financial compensation will be provided to study participants.

[figure not shown]
[figure not shown]

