Appendix I

VAGINAL MORBIDITY AT GYNAECOLOGICAL EXAMINATION

It is advised to manually assess adhesions before inserting the speculum for gynecological examination. In addition to grading, it is mandatory to specify the exact location of toxicity on the provided 3D vaginal map, divided into upper, middle, and lower thirds.

| | |
|---------------------------------------|--|
| Participant ID | |
| Time since last RT | |
| Date | |
| Family status |  no partner  partner |
| Menopausal status |  premenopausal  postmenopausal |
| Smoking status |  Never  Previous  Active |
| WHO performance status |  P0  P1  P2  P3 |
| Specify co-morbidities | |
| Vaginal stricture (CTCAE v. 5) |  None  Asymptomatic; mild vaginal shortening or narrowing  Vaginal narrowing and/or shortening not interfering with physical examination  Vaginal narrowing and/or shortening interfering with the use of tampons, sexual activity, or physical examination |

| | |
|---------------------------|--|
| Vaginal Adhesions | 
 no adhesions
 
 adhesions in the upper third
 
 adhesions in the middle third
 
 adhesions in the lower third
  
Upper third
 
Middle third
 
Lower third
 |
| Vaginal Elasticity | 
 tissue soft and mobile
 
 tissue a little firm and mobile
 
 tissue quite hard with limited mobility
 
 tissue hard and immobile
 
 complete obliteration, not accessible
 |
| Vaginal Fibrosis | 
 no fibrosis
 
 fibrosis in the upper third
 
 fibrosis in the middle third
 
 fibrosis in the lower third
  
Upper third
 
Middle third
 
Lower third
 |

| | | | |
|--|---|--|--------------|

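### Stenosis after pelvic salvage surgery would enter the dose-response model as an event against a radiation dose that does not describe the surgery

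*Protocol*

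**What the plan says.** **Eligibility (Protocol, Study population).** A woman qualifies if she was "Diagnosed with AC and treated with CRT with curative intent" and is "6–36 months post-CRT". Besides not speaking Danish, the exclusions are "History of pelvic radiotherapy for conditions other than the current diagnosis" and "Treatment with electron beam radiotherapy". Nothing refers to recurrence, surgery or further radiotherapy for the anal cancer itself.

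**Data (Data collection, item 2, Clinical data).** The protocol provides for such women: "data on any salvage surgery or recurrence will be collected, along with details of any subsequent treatments provided for the recurrence".

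**Dose (Data collection, item 5).** The vagina is delineated retrospectively on therapy scans and dose-volume histograms are derived. The text does not say which course is meant if there were two, or how two would be combined.

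**Analysis (Statistical analysis plan section of the protocol).** The grade 2 or higher prevalence is taken over all participants, with a 90% confidence interval. On dose-response: "This will be explored using logistic regression, assessing the relationship between radiation dose and vaginal stenosis grade 2 or above", with a spline curve in addition. Neither analysis mentions salvage, recurrence or later treatment.

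**Case report form (Appendix I).** Stricture is graded by its extent and by what it interferes with, and there is no field for its cause. The timing field is "Time since last RT".

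**The concern.** The dose-response question is part of the primary objective (Purpose), and it is the question for which the sample size is justified. It asks whether the radiation dose to the vagina predicts stenosis. A woman examined after pelvic salvage surgery may have narrowing that the operation caused or worsened. Her grade then carries the effect of surgery, while her exposure value is a radiation dose to which surgery adds nothing. The plan would fit her on the same footing as a woman who had chemoradiotherapy (CRT) only.

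The slope could move either way. If salvage is unrelated to vaginal dose, the extra events blur the relationship and pull it towards zero. If larger tumours led both to more vaginal dose and to more salvage, the extra events fall at high dose and the slope is too steep. The Introduction looks towards dose constraints, so a distorted slope matters beyond this study.

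**Working it through.** **1. Does the plan admit these women and leave their later treatment unused?**

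| Step | What the protocol fixes |
|---|---|
| Entry | Curative-intent CRT, 6–36 months earlier; no recurrence-free condition |
| Exclusion | Other pelvic radiotherapy only if given for another condition |
| Expected pool | 318 women, counted as alive; no deduction for recurrence |
| Recording | Salvage surgery, recurrence and its treatment are collected |
| Prevalence | All participants in the denominator |
| Dose-response | Grade 2 or higher on dose; no restriction, covariate or sensitivity analysis for later treatment |

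Salvage surgery is named. A second pelvic course is not; it follows only from the exclusion wording and from the reference to treatments for recurrence.

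**2. The plan's own figure.** The Sample size section states 80% power at about 80 participants for r = 0.3 and alpha 0.05. Sidedness is not given; two-sided is assumed here.
- Noncentral t: 79.3% at 80, which agrees with the plan; 82 are needed for 80%.
- Fisher z: power = Φ(√(n−3) × atanh(0.3) − 1.960). At n = 80 this is Φ(√77 × 0.3095 − 1.960) = 77.5%; 85 are needed for 80%.

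No stated figure depends on how salvage is handled.

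**3. Shift in the pooled prevalence.** Inputs not in the documents, so assumed: share with later pelvic treatment s = 5–15%; grade 2 or higher in those women p1 = 60–100%; in the rest p0 = 25%. Shift = s × (p1 − p0).

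| s (of 80) | p1 = 60% | p1 = 80% | p1 = 100% |
|---|---|---|---|
| 5% (4) | 1.75 | 2.75 | 3.75 |
| 10% (8) | 3.5 | 5.5 | 7.5 |
| 15% (12) | 5.25 | 8.25 | 11.25 |

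Entries are percentage points. The 90% half-width at 25% and n = 80 is 1.645 × √(0.25 × 0.75 / 80) = 8.0 points. The shift exceeds it only at the 15% share with p1 of 80% or more.

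**4. Excess events in the logistic model.** These women also received CRT, so some would have stenosis anyway. Excess = k × (p1 − p0).
- p1 = 100%: 4, 8 or 12 women give 3, 6 or 9 excess events, out of 0.25 × (80 − k) + k = 23, 26 or 29 in total.
- p1 = 60%: the excess is 1.4, 2.8 or 4.2.

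**5. Cost of restricting.** With 76, 72 or 68 women left, Fisher z power for r = 0.3 is 75.3%, 72.9% or 70.4%, against 77.5% at 80. The 90% half-width of the subset prevalence at 25% is 1.645 × √(0.1875/76) = 8.2 points at 76 and 1.645 × √(0.1875/68) = 8.6 at 68.

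**The case against.** **The prevalence is sound as defined.** A reader might infer that the primary prevalence is wrong because it mixes causes. The documents do not support that. The objective concerns women after treatment for localized anal cancer, and the endpoint does not attribute stenosis to CRT alone. An all-participant survivorship prevalence is coherent. This objection stands: the primary estimate should stay, and the subset figure is a supplement.

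**Covariates and sensitivity sets are often left to a separate analysis plan.** This stands in part. The protocol has its own statistical section, which names the endpoint and the model for dose-response and collects the salvage data without using them. Although it does not list the model's analysis set, followed as written it pairs surgical narrowing with radiation dose.

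**Re-irradiation is inferred.** A reader might conclude that re-irradiated women are known to be in the study, with two conflicting clocks because eligibility runs from CRT while the form asks for "Time since last RT". No passage mentions re-irradiation. For a woman with one course the two clocks can be read as the same, and no planned analysis uses the field. This part is conditional on a second course occurring.

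**The size may be small.** The Introduction describes excellent disease control, and no document gives a salvage rate. It would also be wrong to treat every event in a salvaged woman as misattributed, as the 25% background in the working shows. This stands.

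**Restriction has its own bias.** Salvage happens after CRT and may track tumour size and dose, so conditioning on it can introduce selection. This stands, and it is a reason to show both models.

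**Conclusion.** The point holds for the dose-response analysis. Women with pelvic salvage surgery are eligible and recorded, their later treatment has no role in the plan, and any narrowing due to surgery would be modelled as a response to radiation dose. For a second pelvic course the same follows if one occurs; the dose for such a woman is then undefined, because no course is named.

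The size cannot be derived from the documents. Under the assumed 5–15% share and 60–100% against 25%, the pooled prevalence exceeds the prevalence in women without later pelvic treatment by about 2 to 11 points, against a half-width of about 8. The excess is about 1 to 9 events among roughly 21 to 29 (lowest case: 0.25 × 76 + 0.6 × 4 = 21.4). That salvaged women have more stenosis is itself an assumption. The direction of the slope bias is unknown, and if few such women take part the effect is small. The eligibility criteria need not change.

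**What to change.** Change the analysis section; leave the eligibility criteria and the primary prevalence as they are.

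1. Fit the logistic and spline dose-response models in women with no pelvic salvage surgery and no pelvic re-irradiation before the examination. Report the all-participant model as a sensitivity analysis.
2. Report the grade 2 or higher prevalence in that same subset as a supplementary estimate beside the all-participant figure.
3. State that if any woman had a second pelvic course, dose and elapsed time are taken from the primary CRT. Record the date and site of any later pelvic surgery or radiotherapy, so that treatment before and after the examination can be told apart.

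The cost is a few sentences and a small addition to data already drawn from the medical records, with no new procedure for participants. The main model loses a few women: power for r = 0.3 falls from about 77.5% to between 75% and 70% if 4 to 12 of 80 are set aside. Presenting both models lets the reader judge whether selection on a post-CRT event or misattributed events drives any difference.

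### Nothing in the protocol keeps vaginal contouring masked to, or finished before, the morbidity grade, so outcome-aware contouring could bias the dose-response analysis

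*Protocol*

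**What the plan says.** Data collection, item 5 (Radiation Dose parameter) names one contourer and the material: "The principal investigator will retrospectively delineate the vagina on therapy scans from the included participants in accordance with applicable delineation guidelines". It continues that, on this basis, "a retrospective analysis of dose-volume histograms will be performed to identify correlations between vaginal morbidity and radiation exposure".

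The Statistical analysis plan section of the protocol uses logistic regression for "assessing the relationship between radiation dose and vaginal stenosis grade 2 or above", with a spline curve to show any non-linearity. The Purpose section places this in the primary objective, "including the potential dose-response relationship between radiation exposure and morbidity", and the Sample size section justifies about 80 participants by power to detect a dose-stenosis correlation.

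On timing, Inclusion procedures says that "the gynecological examination will either be performed shortly after consent or scheduled for their next follow-up visit". On who grades, Data collection, item 3 provides a seminar for "all relevant physicians responsible for assessments at the three participating centers" to align grading. On access, Data collection, item 2 (Clinical data) says: "Access to these records will be granted to the principal investigator and relevant regulatory authorities for research purposes". Data management puts all data in one REDCap database and describes no separation of dose data from outcome data.

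No section mentions masking of the contourer, pseudonymised scans, or a lock on contours before they are linked to outcomes.

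**The concern.** The exposure in the dose-response analysis depends on a human outline. The delivered dose distribution is fixed, but the contour decides which part of it counts as vaginal dose. If the person drawing it knows which women have stenosis, or in which third of the vagina Appendix I maps the damage, doubtful boundaries can be settled differently in cases and non-cases. The resulting error depends on the outcome.

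Such error can create, exaggerate or hide an association. A larger sample does not cure it, because the spurious difference stays the same size while its standard error shrinks. No later analysis can restore masking once contours have been drawn with grades in view, so this is a data-collection rule for the protocol and not a detail to leave to a separate SAP.

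The protocol already recognises observer effects for the grading, where it plans a seminar. It has no counterpart for the contours. The background presents dose constraints as the eventual use of the results and cites candidate limits of 43 Gy and 48 Gy (for different metrics), so a systematic error of 1 or 2 Gy would not be trivial.

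**Working it through.** **1. What the text fixes and what it leaves open**

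| Question | Protocol |
|---|---|
| Who contours? | The principal investigator (Data collection, item 5) |
| When? | Retrospectively, on scans of included women; order relative to the examination not stated |
| When is the grade recorded? | Soon after consent or at the next follow-up visit (Inclusion procedures) |
| Who grades? | Physicians at the three centers; not stated whether the principal investigator is one of them |
| What may the contourer see? | Medical records (item 2); access to the Appendix I form during contouring neither granted nor barred |
| Safeguard on contours? | Delineation guidelines, not named; no masking and no lock |

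Outcome-aware contouring is therefore neither stated nor prevented.

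**2. The plan's own figure**

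The protocol gives no figure for contouring error. The nearest is the power statement: about 80 women, r = 0.3, alpha 0.05, 80% power. With the Fisher z approximation (two-sided), power = Φ(atanh(0.3) × √77 − 1.960) = Φ(0.3095 × 8.775 − 1.960) = Φ(0.756) = 77.5%. The small shortfall is a separate matter; r = 0.3 serves below only as a yardstick.

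**3. Illustration of sensitivity**

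Inputs: N = 80 is the protocol's target. The protocol gives no prevalence of grade 2 or above, no SD of vaginal dose and no contouring error, so these are assumed: prevalence 20%, 30% or 50%; no true dose effect; and a systematic contour-driven shift of d SD of dose in cases relative to non-cases. The test is a two-sided 5% two-sample t-test on dose, standing in for the planned logistic regression on the same two variables.

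Non-centrality λ = d × √(n₁n₀/N); critical value 1.991 on 78 degrees of freedom; the rejection probability comes from the non-central t distribution. Spurious correlation: r = d√(p(1−p)) / √(1 + d²p(1−p)).

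| Cases / non-cases | √(n₁n₀/N) | d = 0.1 | d = 0.2 | d = 0.4 | r at d = 0.4 |
|---|---|---|---|---|---|
| 16 / 64 | 3.578 | 6.4% | 10.9% | 29.3% | 0.16 |
| 24 / 56 | 4.099 | 6.9% | 12.8% | 36.7% | 0.18 |
| 40 / 40 | 4.472 | 7.3% | 14.3% | 42.4% | 0.20 |

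Example: with 24 / 56 and d = 0.2, λ = 0.2 × 4.099 = 0.820 and the rejection rate is 12.8%. A simulation of the correlation test at d = 0.1 and 0.2 agrees (6-7% and 11-14%).

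In Gy, the shift depends on the assumed SD. If it is 5 Gy, then d = 0.1, 0.2 and 0.4 mean 0.5, 1 and 2 Gy; if it is 10 Gy, they mean 1, 2 and 4 Gy. Because λ grows with √N for a fixed d, more patients raise the false-positive rate.

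**The case against.** A reader might infer that the contours will be drawn by someone who already knows each woman's toxicity, and that the study has chosen to do this unblinded. The documents do not support that. Retrospective delineation means work on existing scans of women already included. As the examination may be deferred to a later visit, some contours could come before the grade. The protocol does not say that the principal investigator performs examinations. The access sentence, "Access to these records will be granted to the principal investigator", concerns medical records; stenosis grade and location go on the separate Appendix I form, so the sentence is not evidence of access to outcomes. These corrections stand in full.

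Other points stand in part. Guidelines narrow the contourer's discretion, but the protocol does not name them, and a guideline does not replace masking. The fixed dose distribution bounds what an outline can change. A single contourer avoids differences between observers, and restricting contouring to included women is no flaw, since only they have an outcome. The dose-response analysis is described as exploratory in manner, yet it sits in the primary objective and carries the sample-size justification.

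It is also fair to say that the illustration rests on assumed inputs and that nothing shows a shift of 0.2 or 0.4 SD to be likely; at 0.1 SD the inflation is slight. Finally, masking could be set out in a working procedure not shown. That is possible, but the protocol has a section on exactly this task, names the person doing it, and gives no such condition.

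**Conclusion.** The point holds as a missing safeguard, not as a demonstrated bias. The protocol makes the exposure a judgement by the principal investigator and relates it to the graded outcome, without ensuring that the two are kept apart. The dose-response analysis is exposed; the prevalence of stenosis grade 2 or higher, the primary endpoint, is not.

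The size cannot be known from the documents. Under the stated assumptions the false-positive rate ranges from barely above nominal (6-7% at 0.1 SD) to 29-42% at 0.4 SD, where the spurious correlation of 0.16-0.20 is more than half the design value of 0.3. These figures show sensitivity and do not predict what will happen. The change should be made because it is cheap and because the error, if it occurred, could not be undone in the analysis.

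**What to change.** In Data collection, item 5, state that:

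- the principal investigator contours pseudonymised scans without access to Appendix I or questionnaire data;
- contours and exported dose-volume values are locked before they are linked to outcomes in REDCap;
- where the principal investigator also examined the woman, her scan is contoured in random order after a delay. This reduces recall but cannot exclude it.

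The cost is a rule on the order of work, a REDCap permission setting, and a small amount of coding by existing study personnel. Someone other than the principal investigator must pseudonymise the scans and hold the key, and the protocol should say which role does so. The tentative schedule has data collection ending in June 2026 and analysis in fall 2026, which leaves room for the lock. Masking does not measure how reproducible the contours are; that is a separate question.
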